4. During the 14-day data collection period, data from the EMA will be collected using EMA software platform on a personal smartphone (iOS or Android) and EMA software platform.⁷³ Each morning, participants will receive an EMA survey concerning asthma symptoms and a reminder to use their spirometer. Additionally, EMA surveys addressing disinfectant use, asthma symptoms, and spirometry will occur randomly twice/day (6am – 10pm) or tailored for those working off hours (Appendix).
5. A custom interface between the EMA platform and the Awair indoor air quality monitor will alert participants when levels of indoor VOCs or particulates are detected outside the optimal range (Table 1). The air quality monitor will communicate with the EMA platform using publicly available application programming interface (api). Upon notification from the Awair, the EMA will signal the participant to complete a brief survey on disinfectant use/air particulate exposure (depending on the alert), current asthma symptoms, and proximity to the Awair (Appendix). The EMA will then direct participants to use the spirometer. Participants experiencing symptoms will be guided to follow their asthma action plan/provider instructions.
6. Thirty minutes after VOC/PM_{2.5} notification, a second EMA notification will be sent for participants to complete a survey on mitigation strategies, respiratory outcomes, and spirometry use if not already completed (Figure 4).
7. Research personnel will monitor use of these devices/apps and contact participants if a 24-hour gap in data is noted to address concerns and determine acceptability. Research team members will check-in with each participant at about the 7-day mark to address technical concerns and ease of use.

8. At the end of the 14 days, participants will complete a short acceptability, appropriateness, and feasibility REDCap survey. A random sample of 20 participants will be interviewed to provide further insights.
9. Participants will be asked to return the Awair in the provided mailer. The Awair will be fully disinfected per manufacturer's directions. Participants will keep the Zephyr_x spirometer as an incentive.

Baseline Measures

The following measures will be administered at baseline via REDCap:

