- *EMA survey triggered by VOCs/PM_{2.5} greater than optimal range as detected by the Awair* will query asthma symptoms, lists of probable sources of elevated VOCs or PM_{2.5}.
- *EMA survey 30-minutes after Awair air quality notification* queries mitigation strategies used (from lists) and asthma symptoms.
- *Home spirometer use* (Yes:No) queried in each EMA survey

Home spirometer. FEV₁% predicted– a standard metric of lung function for those with asthma.

Seven-Day check-in. Open-ended questions to identify any trouble-shooting areas, determine if adjustments need to be made, and assess ease of use of the app/devices. Interactions will be recorded and reviewed by the research team for patterns and to identify any adjustments that are needed.

Participant feasibility assessment. At the end of the 14-day data collection period, participants will be asked to respond to a short REDCap survey assessing acceptability, appropriateness, and feasibility of the indoor air quality monitor, EMA notifications, and the home spirometer with response ranging from 1=completely disagree to 5=completely agree. A random sample of 20 participants will be interviewed to further explore these factors using open-ended questions such as "Tell us what you liked/didn't like about the indoor air quality monitor", "Describe the strengths/concerns about the survey you received about your home indoor air quality".

Data Analysis

Each day of observation will be divided into four 4-hour periods between 6 a.m. and 10 p.m. Data from a given period will be considered as follows:

1. Period specific data from all event-contingent EMA prompts [prompts triggered by high indoor air VOC/PM_{2.5} readings] will be analyzed. If multiple event-contingent prompts were answered, data will be averaged across all event-contingent prompts during that period.
2. Data from all answered baseline and random [signal-contingent] EMA prompts will be considered.

Aim 1. For this aim, we will assess:

1. Compliance with the EMA prompts as indicated by the frequency of responses to prompts, specifically:
 - a. # of responses (complete:incomplete)/number of prompts
 - b. # times spirometer used/number of prompts
 - c. # times environment modified/number of event-contingent prompts
2. Compliance as described in 1a-1c by 4-hr each period.

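### Compliance measures 1a and 1b by 4-hour period pool prompt types whose mix differs between periods, so a prompt-type difference could be misread as a time-of-day difference

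*Combined protocol and SAP*

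**What the plan says.** The Procedures section, steps 4 to 6, sets up four kinds of prompt with different timing:

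- Morning survey: "Each morning, participants will receive an EMA survey concerning asthma symptoms and a reminder to use their spirometer". No clock time is given.
- Random surveys: these "will occur randomly twice/day (6am – 10pm) or tailored for those working off hours".
- Alert surveys: an interface with the air monitor "will alert participants when levels of indoor VOCs or particulates are detected outside the optimal range", and the participant is then surveyed and directed to the spirometer.
- Follow-up: thirty minutes after an alert, "a second EMA notification will be sent for participants to complete a survey on mitigation strategies". It also covers respiratory outcomes, and spirometry if that has not yet been done.

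The Data Analysis section then states: "Each day of observation will be divided into four 4-hour periods between 6 a.m. and 10 p.m". Under Aim 1, measure 1a is the number "of responses (complete:incomplete)/number of prompts" and measure 1b is the number of "times spirometer used/number of prompts". Neither denominator is limited to a type of prompt. Measure 1c, changes made to the environment, is divided by event-contingent prompts only. Item 2 repeats all three by period: "Compliance as described in 1a-1c by 4-hr each period".

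The data rules at the head of that section do separate event-contingent prompts from baseline and random ones. That separation is kept in 1c but not in 1a or 1b.

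**The concern.** A breakdown by clock period invites the reader to ask whether participants comply better at some hours than at others. For 1a and 1b the periods do not contain the same thing. The morning period or periods hold a once-daily survey paired with a spirometer reminder; the later periods hold none. Alert and follow-up prompts depend on air readings, so nothing in the schedule spreads them evenly.

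If people respond differently to different kinds of prompt, the pooled ratio will vary by period even when the hour has no influence. For 1b there is a second route. The follow-up asks for spirometry only where it is still outstanding, so a participant who does everything requested records one spirometry for two prompts. Periods with a larger share of follow-ups then show a lower 1b without any lapse in compliance.

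At stake is the reading of one descriptive feasibility table in a study meant to supply preliminary data for a powered one.

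**Working it through.** The plan gives no compliance target or by-period figure, so there is nothing to reproduce. The check is arithmetic on the prompt schedule.

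**Inputs from the protocol.** One morning survey and two random surveys per day; four periods; 14 days; fifty participants (Sample section).

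**Assumptions.** All fifty take part for the full 14 days. Random prompts spread evenly, so 2/4 = 0.5 per period per day. All morning surveys fall in 6–10 a.m. The number of alert plus follow-up prompts per period per day, *e*, is the same in every period and is varied. Response rates are illustrative and do not vary by hour.

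**Step 1: scheduled mix.** Per person there are 3 × 14 = 42 scheduled prompts, or 42 × 50 = 2,100 in all.

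- 6–10 a.m.: (1 + 0.5) × 14 × 50 = 1,050, of which 1/1.5 = 67% are morning surveys.
- Each other period: 0.5 × 14 × 50 = 350, of which 0% are morning surveys.

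**Step 2: spurious gap in 1a.** Let the morning rate be p_m and the rate for every other prompt be p_o. The morning share in 6–10 a.m. is s = 1/(1.5 + e). Pooled compliance there is s·p_m + (1 − s)·p_o, against p_o elsewhere, so the gap is s × (p_m − p_o). With p_o = 70%:

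| Morning rate | e = 0 (s = 67%) | e = 1 (s = 40%) | e = 4 (s = 18%) |
|---|---|---|---|
| 90% | +13.3 | +8.0 | +3.6 |
| 80% | +6.7 | +4.0 | +1.8 |
| 70% | 0 | 0 | 0 |
| 60% | −6.7 | −4.0 | −1.8 |

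The entries are percentage points. For example, at 90% and e = 0: (1 × 0.90 + 0.5 × 0.70)/1.5 = 83.3%, against 70.0%. Tabulated within prompt type, every gap is 0 by construction.

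**Step 3: morning surveys on both sides of 10 a.m.** If half are sent after 10 a.m., the first two periods each have a morning share of 0.5/(0.5 + 0.5) = 50%. At 90% and 70% with no alerts, both show 80% and the last two show 70%. The distortion moves to morning against later; it does not go away.

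**Step 4: uneven alerts.** Leave the morning survey out. Assume random prompts are answered at 70%, alert-type prompts at 50%, and e = 0.2, 0.5, 0.5 and 1.5 across the four periods. Pooled rates are (0.5 × 0.70 + e × 0.50)/(0.5 + e) = 64.3%, 60%, 60% and 55%. The pattern comes from the mix alone.

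**Step 5: 1b under perfect compliance.** Assume one alert and one follow-up per period per day, and one spirometry at every morning, random and alert prompt, so that none is outstanding at the follow-up.

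- 6–10 a.m.: (1 + 0.5 + 1)/(1 + 0.5 + 1 + 1) = 2.5/3.5 = 71%.
- Other periods: (0.5 + 1)/(0.5 + 1 + 1) = 1.5/2.5 = 60%.

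That is a gap of about 11 points with no missed spirometry and no effect of the hour.

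**The case against.** The strongest reply is that this is a plain descriptive breakdown. No test, threshold or interpretation is attached to compliance by period, and time of day enters the plan as a covariate only in the Aim 3 models, where compliance is not an outcome. That is correct. A reader might infer that the investigators will report a time-of-day effect, or that a later study will choose its prompt times from this table. The documents say neither, so the point is only that the table could be misread.

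Three further limits stand.

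- A reader might take item 2 to be affected throughout. It is not: morning surveys cannot enter the denominator of 1c.
- A reader might suppose that the morning survey certainly falls in the first period. The text names only the morning, the 10 a.m. boundary lies within it, and prompting may be tailored for people who work off hours. Step 3 shows what changes.
- A reader might suppose that alerts bunch at known hours because cooking and cleaning raise the readings. The documents link those activities to particulates or VOCs but do not say when in the day they happen. Step 4 is therefore only an illustration.

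It is also fair to say that the size in 1a depends on response differing by prompt type, for which the documents give no evidence, and that frequent alerts dilute the gap. Participants are selected for using disinfectants or cleaners at least five times a week, so alerts may be common.

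The data rules' separation of event-contingent prompts does not settle the matter. It is not carried into 1a or 1b, and it groups baseline prompts with random ones.

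**Conclusion.** The point holds for 1a and 1b and is minor. As written, both pool prompt types whose mix differs by period, so a contrast between periods is mixed with a contrast between prompt types.

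The unequal scheduled mix follows from having a morning survey at all, given evenly spread random prompts. The size of any resulting gap in 1a is not known. On the stated assumptions it ranges from +13.3 points through 0 to −6.7 for 6–10 a.m., and shrinks as alert prompts are added. No single value in that range should be quoted as the expected bias. For 1b a gap can arise under perfect compliance, 71% against 60% in the example, assuming one alert pair per period per day and one spirometry per pair.

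Nothing here affects 1c through the morning survey. The documents do not support a claim that a false time-of-day effect will be reported.

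**What to change.** In Aim 1, item 2, state that 1a and 1b will be reported by 4-hour period within prompt type, with separate lines for morning, random, alert and 30-minute follow-up prompts. State that any comparison across the day will use the random prompts. They are the cleanest basis, because the response to the morning survey cannot be separated from the hour at which it is sent.

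This takes a sentence of SAP wording and a different table layout, with no new data. The price is a longer descriptive table with smaller cells: on the assumptions above, the random-prompt comparison rests on about 350 prompts per period.

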Zephyr_x Spirometer⁷² system allows for laboratory quality pulmonary function tests (PFTs) at home (FVS-forced vital capacity, FEV₁-forced expiratory volume in 1 second, FEV₁/FVC, flow-volume loop). The system consists of an FDA approved handheld Bluetooth spirometer (MIR Spirobank Smart), and a mobile application that works on a smartphone or tablet device. The MIR Spirobank bank measures 49x109x21 mm and weighs 60.7 g. Participants share PFT results through their app and researcher team members will access a HIPAA compliant portal to view participants' PFT results in real time. An in-App video coaching feature guides the participant through the PFT maneuver. Each maneuver conducted by the participant creates a time and date stamped American Thoracic Society standard PFT report accessible through the portal. Data will be exported from the dashboard to a .CSV file.

Procedures (Figure 3)

1. Randomly selected individuals from the CGAS study who meet eligibility criteria will be invited to participate in the current study. Those interested will be directed to a REDCap link to complete an E-consent form and baseline questionnaire.
2. An Awair Indoor Air Quality Monitor and a Zephyr_x Spirometer will be mailed to each participant along with a quick start guide, written instructions with a link to an instructional video, and research team contact information. Once received, a research team member will conduct a live chat with each participant to enable the devices, download apps (EMA, Zephyr_x), setup and test the devices and apps, review the protocol, and address questions. Participants will be instructed to place the portable Awair air quality monitor in the room where they spend the most time during the day and at night where they sleep.
3. A 3-day run-in period will be completed during which the participants will become familiar with the devices and troubleshoot issues (Awair requires 24-48 hours to calibrate VOC sensors). Study personnel will be available to answer questions/address technical issues. After the run-in period, a research team member will contact the participant to launch the 14-day data collection period.

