We will also assess the duration the indoor air quality monitor is used by each participant. The quantitative participant feasibility assessment of acceptability, appropriateness, and feasibility will be analyzed descriptively. In addition, we will examine differences in use/acceptance by participant characteristics (e.g., age, asthma symptoms, overall health, education, etc). Qualitative interview data will be transcribed, uploaded into Dedoose qualitative analysis software for content analysis.

Aim 2a: We will collect baseline data on the current frequency and degree of disinfectants/cleaners and exposure to environmental triggers (e.g., secondhand smoke). We will capture real-time self-reported data on disinfectant use throughout the study period. We will determine the prevalence of disinfectant/cleaner use and frequency (% EMA prompts at which disinfectant/cleaner use is reported). We will obtain data from the Awair dashboard to determine the number of times VOCs and PM_{2.5} levels exceed optimal levels, average daily levels, average levels per time period, and fluctuations in VOC and PM_{2.5}. We will identify possible environmental triggers that contribute to high levels of VOCs and PM_{2.5} leading to event-contingent prompts.

[figure not shown]
Aim 2b: We will determine baseline level of asthma control as measured by the ACT. We will use EMA to determine the level of asthma control over the study period as indicated by (a) asthma symptoms reported at each prompt and over the 14 days; (b) number of time-periods during which an EMA prompt is sent and participants report asthma symptoms; and (c) lung function as measured by FEV₁% predicted at each prompt. Asthma control will also be evaluated using EMA by exploring differences in variability in lung function.

Aim 3: Data collected using the EMA approach are multilevel with time windows (level 1) nested with individuals (level 2). The exposure variables will include: (1) Baseline self-reported use and frequency of disinfectant/cleaner use and PM_{2.5} exposures; (2) Number of times VOC and PM_{2.5} levels exceed the threshold for the optimal readings per week; and (3) Average scores of VOC and PM_{2.5} levels in the time windows considered in the analysis. The outcome variables we will consider include occurrence of any asthma symptoms, inhaler use, and FEV₁% predicted (within 30 minutes of each EMA prompt).

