We will use multi-level binary logistic regression to examine the associations of the exposure variables with the binary outcome variables. We will use multilevel linear regression to examine the associations of the exposure variables with FEV₁% predicted. We will control for level 1 variables (time of day, day of week) and level 2 variables (baseline asthma symptoms, demographic characteristics, and psychosocial characteristics). Using available time stamps from the indoor air quality monitor, EMA, and the spirometer, we will also explore average lag time between an event-contingent prompt and self-reported asthma symptoms using multilevel survival analyses.

Summary

The proposed study has several strengths. First, our study is innovatively addressing the increased use of disinfectants during COVID-19 in adults with asthma. The study builds on an ongoing study and will be conducted with individuals who have agreed to be recruited for future studies and facilitate recruitment. Furthermore, participants will be drawn from a wide geographic area in the US which increases broad representation of participants. Moreover, we will uniquely gather real time environmental exposure data and indicators of asthma control in unregulated indoor residential space without actual in-person contact. Finally, findings from this study have the potential to impact recommendations for indoor use of disinfectants/cleaners for those with asthma and will guide further research.

References

1. Center for Disease Control and Prevention. Asthma. FastStats web site. <https://www.cdc.gov/nchs/faststats/asthma.htm>. Published 2018. Accessed Date.
2. Center for Disease Control and Prevention. AsthmaStats. https://www.cdc.gov/asthma/asthma_stats/default.htm. Published 2020. Accessed Date.
5. Center for Disease Control and Prevention. Coronavirus (COVID-19). <https://www.cdc.gov/coronavirus/2019-nCoV/index.html>. Published 2020. Accessed Date.

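### Aim 3 sets out no within-person correlation across windows and days; with a person intercept alone, standard errors for time-varying exposures would be too small if exposure and outcome both persist

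*Combined protocol and SAP*

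**What the plan says.** All of this is in the Data Analysis section unless noted.

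- **Structure (Aim 3).** "Data collected using the EMA approach are multilevel with time windows (level 1) nested with individuals (level 2". The windows are defined at the start of the section: "Each day of observation will be divided into four 4-hour periods between 6 a.m. and 10 p.m".
- **Rows of data.** Where several event-contingent prompts are answered in one window, "data will be averaged across all event-contingent prompts during that period". For the others the text says only: "Data from all answered baseline and random [signal-contingent] EMA prompts will be considered".
- **Models (Aim 3).** For FEV1% predicted: "We will use multilevel linear regression to examine the associations of the exposure variables". Binary outcomes get the logistic counterpart. Time of day and day of week enter as covariates, with person-level adjusters.
- **Exposures (Aim 3).** There are three kinds: baseline self-report, weekly counts of threshold exceedances, and average levels within windows.
- **Schedule (Procedures, steps 3, 4 and 6).** Data are collected for 14 days. "Each morning, participants will receive an EMA survey concerning asthma symptoms and a reminder to use their spirometer". Two random prompts a day are added, and for alerts: "Thirty minutes after VOC/PM_{2.5} notification, a second EMA notification will be sent".

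No day level, residual covariance, lagged outcome or robust standard error is mentioned anywhere.

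**The concern.** A person intercept accounts for stable differences between people. It does not account for one person's bad day, or for a home whose air stays poor through an afternoon and evening. Time of day and day of week as covariates remove only patterns common to all participants. If room air and respiratory state both carry over from one window to the next, neighbouring windows repeat part of the same information, and a model that counts them as separate given the person overstates its precision.

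The Specific Aims say that the findings are to supply preliminary data for a powered study, and the Summary says they may affect recommendations on disinfectant use. Intervals that are too narrow would make the exposure associations look firmer than they are. The point estimates are not in question here.

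**Working it through.** The plan gives no standard error, intraclass correlation or autocorrelation for Aim 3, so there is no figure to reproduce. The check asks how far a person-intercept model would misstate the standard error under assumed correlations.

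**Inputs from the plan.** 50 people; 14 days × 4 windows = 56 windows per person. The 6–10 p.m. window and the next 6–10 a.m. window have midpoints 12 hours apart, which is three 4-hour steps.

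**Assumed.** Lag-1 (4-hour) correlation rx for the exposure and ry for the outcome residual, each 0.3, 0.5 or 0.7; 75% of windows answered.

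**Step 1: formula for a window exposure and a linear outcome.** Let p = rx × ry. Within a day there are 3, 2 and 1 pairs of windows at lags 1, 2 and 3. Between one day and the next there are 1, 2, 3, 4, 3, 2, 1 pairs at lags 3 to 9. Per day this gives

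S = 3p + 2p² + 2p³ + 2p⁴ + 3p⁵ + 4p⁶ + 3p⁷ + 2p⁸ + …

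(the terms from lag 9 on add less than 0.01 even at p = 0.49). With share a answered, in large samples,

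true SE / reported SE: k = √(1 + 2aS/4) = √(1 + aS/2)

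and the real error rate of a nominal 5% test is 2[1 − Φ(1.96/k)].

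**Step 2: numbers, with a = 0.75.**

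| rx / ry | p | S | k | Type I error | Simulated k | Simulated type I error |
|---|---|---|---|---|---|---|
| 0.3 / 0.3 | 0.09 | 0.288 | √1.108 = 1.05 | 6.3% | 1.05 | about 6% |
| 0.5 / 0.5 | 0.25 | 0.918 | √1.344 = 1.16 | 9.1% | 1.14 | about 9% |
| 0.7 / 0.7 | 0.49 | 2.475 | √1.928 = 1.39 | 15.8% | 1.43 | about 17% |

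The simulated columns come from data sets with 50 people, 56 windows, 75% answered and the overnight gap. With every window answered (a = 1) the formula gives 1.07, 1.21 and 1.50. Treating all windows as evenly spaced, √((1+p)/(1−p)), would give 1.09, 1.29 and 1.71, so the overnight gap matters.

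**Step 3: the three kinds of exposure.** A separate large-sample calculation for the random-intercept linear model (complete data, four windows a day, intraclass correlation 0.3 to 0.7, which hardly matters) gives reported SE / true SE:

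| Exposure | ry = 0.2 | ry = 0.4 | ry = 0.6 |
|---|---|---|---|
| Baseline | 1.00 | 1.00 | 1.00 |
| Window average, rx = 0 | 1.00 | 1.00 | 1.00 |
| Window average, rx = 0.6 | 0.91 | 0.84 | 0.76 |
| Weekly count, week by week | 0.86 | 0.73 | 0.59–0.60 |

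The type I error is 7.3%, 10.2% and 13.7% in the third row, and 9%, 15% and 24–25% in the fourth. The Step 1 formula agrees: at 0.6/0.6, p = 0.36, S = 1.496 and k = √1.748 = 1.32, whose inverse is 0.76. With three windows a day the ratios are milder: 0.96, 0.91, 0.84 for window averages at rx = 0.6, and about 0.92, 0.82, 0.68 for weekly counts. A person-day effect in place of serial correlation, at 10% to 40% of within-person variance, gives 0.94 to 0.80 for window averages at rx = 0.6.

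**Step 4: binary outcomes.** Simulated random-intercept logistic models at 0.6/0.6 give ratios of 0.94 and 0.88 (latent serial term with SD 1 and 2) and type I error of 6.0% and 7.7%. This is milder than the linear 0.76 and 13.7%.

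**Step 5: person-clustered standard errors.** In the same logistic runs the ratios become 1.00 and 0.98, and the type I error 5.5% and 5.8%. For linear outcomes, type I error comes to about 4–5% for window exposures and about 7% for weekly ones.

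**The case against.** The strongest reply is that the plan is silent and has not chosen independence. A two-level linear mixed model can carry a serial residual without a word of the text changing. That is fair, and a reader who infers that the plan asserts independent windows goes further than the documents do. But the text is all an analyst has to follow, and the plain model it describes has person effects only.

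A reader might also infer that prompts 30 minutes apart are analysed as independent rows. The documents do not support this. Level 1 is the 4-hour window, and multiple event-contingent answers in a window are averaged, which would merge most alert and follow-up pairs if the follow-up counts as event-contingent. Two things remain. Scheduled prompts have no merging rule while FEV1 is tied to each prompt, and averaging within a window does nothing about correlation between windows and days.

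A third inference, that Aim 3 standard errors are too small throughout, is wrong. Baseline exposures are unaffected by this mechanism, as are window exposures without autocorrelation. Weekly counts are affected only if entered week by week; a single average per person would behave like a baseline exposure.

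Finally, every correlation used here is assumed, Aim 3 is exploratory, and the plan sets no significance level or decision rule for it. That limits the consequence but not the direction of the error.

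**Conclusion.** The point holds for the time-varying exposures, on the condition that the models are fitted with a person intercept only and that exposure and outcome residuals are both positively autocorrelated. Both kinds of persistence are plausible for indoor air and asthma, but the documents do not measure either.

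For FEV1% predicted on window-average VOC or PM2.5, the true standard error is about 1.05 to 1.4 times the reported one, and type I error about 6% to 17%, for assumed lag-1 correlations of 0.3 to 0.7 with 75% of windows answered. Week-by-week exceedance counts fare worse at the same residual correlation; symptoms and inhaler use fare better. With no residual correlation there is no inflation. A simple, nearly free method avoids the problem, so this is more than a request for detail. The consequence is confined to how much certainty is attached to exploratory estimates.

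**What to change.** State in the Aim 3 analysis that all models will report standard errors clustered by person, with a small-sample correction suited to about 50 clusters. The residual error rate of about 7% for weekly counts is a reason to include that correction. For FEV1% predicted, a continuous-time AR(1) residual or a day-within-person intercept can be added as a sensitivity analysis. Fitting both at once is not necessary and may be hard to support with three or four observations a day. It would also help to say whether weekly counts enter week by week, and how scheduled prompts falling in the same window are combined.

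The cost is a model option and somewhat wider intervals. No new data and no change to procedures are needed.
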